**Aim 2: To assess the substitutability of menthol cigarette alternatives.** [*H2a: A significantly higher portion of product preference selections for Phase 2 will favor nmC than all other alternatives. H2b: Participants' use of study products will significantly increase over the one-week substitution period. H2c: Under simulated UBMC ban conditions, >80% of participants will substitute at least 50% of their UBMC use with study product.]*

**Aim 3: To evaluate which product characteristics and perceived effects influence greater substitution.** *H3: Participants reporting higher product satisfaction, including "throat hit", menthol-specific sensory effects,*

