**Figure 2. Study Overview**

in-person lab visits. At the beginning of each visit, pregnancy tests will be completed to ensure that the participant is not pregnant. During visit 1, participants will complete a PROP taste test to measure a participants' perceived intensity to taste. In *Phase 1*, utilizing a randomized crossover design, participants will complete [4 smoking sessions,] each session smoking a different product examining each [participants' puff topography while sampling the product, the product's ability to suppress nicotine craving/withdrawal, and the product's demand indices. Products will include participants' usual brand menthol cigarette (UBMC) as well as 3 commercially-available alternatives, including an mFLC, a pre-assembled mRYO product (menthol tobacco + menthol tube), and an nmC.] All sessions will occur following 12-hrs of nicotine abstinence and be separated by 48-hrs. Participants will complete daily diaries for one-week during this period to more accurately assess current use of their UBMC. In *Phase 2*, participants will [select their preferred study product from Phase 1] and be instructed to completely substitute the product for their UBMC for one week. Participants will complete daily diaries during this period to more accurately assess degree of substitution and perceived effects in real-time. In *Phase 3*, participants will complete a final in-lab visit to assess the substitutability of their preferred product, under simulated ban conditions using a progressive ratio task. In all phases, multiple domains of abuse liability will be assessed, including product administration (in-lab puff topography and daily diary self-report measures), product liking and craving and withdrawal suppression (in-lab and daily diary self-report), and hypothetical purchase tasks to simulate demand.

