## Addiction and Behavior Related to Menthol Cigarette Substitutes

approximately 2 hours each. During this period, participants will complete one week of daily diaries to assess their usage of UBMC.

Preferred Study Product *Ad libitum*-Observational Use Period (Phase 2): During the preferred study product observational use period, participants will be provided products at no cost. Study products will be provided in a 1.2 to 1 ratio based on self-reported use at the time of screening. This slight over appropriation helps to ensure that participants have enough study product available so to not artificially limit use, while also not oversupplying and potentially artificially increasing use beyond what would be usual. Participants will be instructed to completely switch and exclusively use the study product during the 1-week time period. During this period, participants will complete one week of daily diaries. If the participant has not responded after 3 prompts, the assessment will be recorded as missed.

Final Lab Session – Simulated Menthol Cigarette Ban Using a Progressive Ratio Task (Phase 3): Following the one-week use period, participants will come to the lab following 12-hr nicotine abstinence confirmed by eCO. To simulate the effect that restricting menthol in cigarettes would have on increasing (or not) preference for other alternative menthol substitutes, participants will complete a 90-minute concurrent choice task with differential cost (effort) required to earn 2 puffs from their UBMC (10 clicks increasing to 7200 ) versus their preferred study product (always 10 clicks) from Phase 2. This session will last approximately 3 hours.

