
**Addiction and Behavior Related to Menthol Cigarette Substitutes**

-0.2 indicates complementarity, and CPE between -0.2 and 0.2 indicate independence of the two products. Consistent with previous studies conducted by [name], the PR task will simulate the effect that restricting menthol in cigarettes would have on increasing (or not) preference for other alternative menthol substitutes. Participants will complete a 90-minute concurrent choice task with differential cost (effort) required to earn the reinforcement (2 puffs) from their UBMC and the study product (mFLC,mRYO or nmC). Puffs from the study product can be earned by clicking a computer mouse 10 times on a picture of the study product, but to earn two puffs of the UBMC, they will be required to make escalating response requirements (computer mouse clicks) according to the following schedule: 10, 160, 320, 640, 1280, 2400, 3600, 4800, 6000, 7200. A maximum of 10 reinforcers (20 puffs) per session will be allowed. The proportion of reinforcers earned is considered to provide an index of the strength of the reinforcing effects of the product. Participants will be informed of the differential sequence between products and instructed that the sessions are 3 hours in length no matter how much or how little they respond. Daily diaries will assess UBMC/study product smoked per day, product satisfaction and pleasure (see Table 1 for specific daily diary measures). [Substitution assessed via use behavior during Phase 2 will be operationalized as the ratio of study product to UBMC used, with a ratio > 0 indicating any substitution and a ratio > 1 indicating substitution of study product for the UBMC at least 50% of the time.]

Table 1. Measures

Measures	Phase 1:			Phase 2:	Phase 3:
	3 in-lab visits			1-week	Final Lab
	Visit 1	Visit 2	Visit 3	Visit 4	Visit 5
Background Measures					
Exhaled CO Abstinence verification	X	X	X	X	X
Pregnancy Test	X	X	X	X	X
Exhaled carbon monoxide	X	X	X	X	X
Breath Alcohol Concentration (BrAC)	X	X	X	X	X
Taste testing strips (PROP)	X				
Sociodemographic measures	X				
Cigarettes Use/Tobacco Use Hx (EDSHC)	X				
Menthol Subscales	X				
Readiness Rulers	X				
Product Use Status	X				
Product Use Detailed Assessment	X				

Addiction and Behavior Related to Menthol Cigarette Substitutes

Fagerstrom	X				
Abuse liability					
Smoking topography	X	X	X	X	
Drug Effects/Liking Questionnaire	X	X	X	X	X

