### **1. Potential Risks and Protections Against Risk**

There are minimal risks associated with this protocol. The protocol requires menthol smokers 21 to 50 years of age and older to undergo 12 hours of tobacco/nicotine abstinence on six occasions and to attempt to substitute another combusted mentholated nicotine product for their current combusted mentholated nicotine product. Tobacco/nicotine abstinence can lead to withdrawal symptoms that include irritability, anxiety, restlessness, hunger, and difficulty sleeping. The effects can be uncomfortable but are not dangerous. Risks and side effects related to the cigarette products that are commercially available include:

- Nicotine addiction: Nicotine is a highly addictive chemical found in cigarettes, and toxic at certain doses. It negatively affects the brain, nervous system and heart, and excessive exposure can result in poisoning, particularly in young children and pets. It also causes blood vessels to contract, increasing your blood pressure and pulse rates.
- Chronic diseases including COPD, bronchitis, emphysema, coronary heart disease, stroke and cancer.
- Smoking can also cause infertility and peptic ulcer disease, as well as slow the healing of wounds. It's the leading cause of preventable illness and death in the U.S.

The risk associated with substituting one combustible menthol product for another is also low. It is very unlikely that there is any difference in the level of harm between the participants' usual brand and the study products; therefore, substitution is unlikely to increase participants' exposure to harmful constituents over their usual brand. We are also attempting to mitigate the risk of artificially increased use due to receiving product by only giving participants study products in a 1.2 to 1 ratio.

We will withdraw participants who become pregnant, begin to breastfeed or receive diagnosis for a cardiovascular disease during the course of the study.

The risk of undermining smoking cessation is also potential risk; however, we will only recruit smokers not currently engaged in a smoking cessation attempt, and we will provide all participants at the end of the study with a referral to the Ohio Tobacco Quit Line ([name]).

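### The Phase 2 substitution ratio measures study product's share of that week's smoking, not displacement of usual menthol cigarette use as H2c words it

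*Combined protocol and SAP*

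**What the plan says.** D.3 Measures defines the outcome: "Substitution assessed via use behavior during Phase 2 will be operationalized as the ratio of study product to UBMC used". Two cut-offs follow. Any value above 0 is read as some degree of substitution, and the higher cut-off is "a ratio > 1 indicating substitution of study product for the UBMC at least 50% of the time". Both counts come from the Phase 2 diary week, and usual UBMC use does not appear.

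H2c (A. Specific Aims, Aim 2) predicts that ">80% of participants will substitute at least 50% of their UBMC use with study product", under a simulated UBMC ban. E.1 Power Analysis ties H2c to Phase 2: with 80 participants it claims 81% power around an 80% share of participants who use the chosen alternative more than half the time. E.2 tests H2c by goodness of fit against 80%.

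Usual use is measured. D.1 says "Participants will complete daily diaries for one-week during this period to more accurately assess current use of their UBMC", and Table 1 lists diary product counts in both weeks. E.2 uses baseline consumption only as a covariate, in the H2b model and by reference in the H3 model.

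On supply, D.2 says "Study products will be provided in a 1.2 to 1 ratio based on self-reported use at the time of screening", free of charge, with an instruction to switch fully. Section G presents the 1.2 to 1 supply as a way to "mitigate the risk of artificially increased use due to receiving product".

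**The concern.** Replacing half of one's UBMC use means smoking fewer UBMC than before. The ratio has no before in it. It shows which product made up most of that week's smoking, and it gives the same answer whether study product displaced menthol cigarettes or was added to them.

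For a menthol ban these outcomes mean different things. The protocol draws the distinction itself for the cross-price task, where elasticity is sorted into substitution, independence and complementarity. The Phase 2 ratio has no such category. If total smoking rises during the week of free product, some participants counted towards the 80% comparison in H2c will have cut their UBMC use by less than half.

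**Working it through.** **Inputs.** B = usual UBMC/day. U and S = UBMC/day and study product/day in Phase 2. R = S/U (D.3). Cut-offs are R > 1 and R > 0 (D.3). Supply limit is S ≤ 1.2B (D.2), assuming that screening use equals B. T = (S + U)/B, total use relative to usual, taking usual use to be UBMC (eligibility requires more than 90% menthol use).

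**The plan's own figures.** R = 1 gives S/(S + U) = 1/(1 + 1) = 0.50. The 50% in D.3 is therefore right as a share of Phase 2 use. For power, an exact two-sided binomial test of 0.80 with n = 80 and alpha 0.05 (two-sidedness assumed) rejects at 56 or fewer, or 72 or more, successes. Its power at a true 0.66, the lower end of the quoted range, is 80.8%, which matches the stated 81%.

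**From share to displacement.** At R = 1, U = S = TB/2. The UBMC reduction is 1 - U/B = 1 - T/2, and S/B = T/2.

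| T | UBMC reduction at R = 1 | S/B at R = 1 |
|---|---|---|
| 1.0 | 50% | 0.50 |
| 1.2 | 40% | 0.60 |
| 1.4 | 30% | 0.70 |
| 1.5 | 25% | 0.75 |
| 1.6 | 20% | 0.80 |
| 1.8 | 10% | 0.90 |
| 2.0 | 0% | 1.00 |

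Every S/B in the table is below 1.2, so the supply permits each case. At constant total use (T = 1) the ratio rule and a rule of U ≤ 0.5B agree, except exactly at R = 1.

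**Examples with B = 20/day (supply 24/day).**
- U = 12, S = 13: R = 13/12 = 1.08, passes; UBMC reduction 1 - 12/20 = 40%; T = 25/20 = 1.25.
- U = 20, S = 21: R = 21/20 = 1.05, passes; reduction 0%; T = 41/20 = 2.05.

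**Any substitution.** With U = B and one study cigarette smoked, R > 0. This is scored as substitution although UBMC use has not changed.

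**The reverse error.** With B = 10, U = 3 and S = 2.5, R = 0.83 fails although UBMC use fell by 70%. Against a rule based on reduction alone, errors therefore run both ways. Against a rule requiring both S > U and U ≤ 0.5B, everyone who passes also passes R > 1, so the present rule can only overcount.

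**Leverage on the H2c test.** If exactly 80% truly met the combined rule, that is 64 of 80. The upper rejection point is 72, so 72 - 64 = 8 overcounted participants (10% of 80) would turn a true 80% into a significant excess. This shows sensitivity; it does not estimate how many would be overcounted.

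**The case against.** **Added use may be uncommon.** Participants are told to switch completely, and the 1.2 to 1 supply is presented as a limit on over-use. The instruction does lower the risk. But the ratio is there to measure how far people switched, so it cannot assume that they did. The limit also leaves room for every case in the table.

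**The share measure is coherent.** D.3 and E.1 both describe use more than half the time, and they agree with each other. This stands: the ratio is a valid share measure. What fails is treating it as the displacement that H2c describes.

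**H2c may not use this ratio.** Its reference to a simulated ban could mean the Phase 3 progressive ratio task. E.1 points to Phase 2, but the text leaves doubt that the sponsor should remove.

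**Other analyses cover it.** The baseline covariate adjusts a model but reclassifies nobody. The cross-price and progressive ratio tasks are separate measures and do not correct the diary outcome.

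**A baseline rule has faults too.** These stand and shape the fix. With B = 10, one UBMC and 1.5 study products per day is a 90% reduction with S > U, yet study product replaced only 15% of usual use; most of the change is cutting down. At minimum 48-hour spacing, sessions fall on days 0, 2, 4 and 6, with abstinence beginning on the evenings of days 1, 3 and 5. Dropping all of these leaves one clean day among days 1 to 7, and none among days 0 to 6. The 12 hours of abstinence before Visit 5 can also fall in the Phase 2 week.

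**Conclusion.** The concern holds as a mismatch between measure and hypothesis. The ratio is study product's share of Phase 2 smoking. It equals a 50% fall in UBMC use only when total use is unchanged; otherwise the reduction at the cut-off is 1 - T/2. A ratio above 0 does not show that anything was substituted.

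Three stronger readings are tempting, and the documents do not support them:
- That nearly unchanged menthol smoking will commonly pass. This needs total use of about 1.8 to 2.0 times usual, which the supply allows but nothing suggests is typical. A 20% to 40% reduction scored as at least 50% needs a smaller rise (T above 1.2 to 1.6).
- That the H2c share is biased upward by a known amount. Upward bias is possible, but no frequency of added use is given.
- That H3 models a misclassified outcome. E.2 does not say that H3 uses the dichotomised ratio.

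The conclusion assumes that screening use approximates usual use and that H2c is scored on the Phase 2 diaries, as E.1 implies. If H2c belongs to Phase 3, the D.3 labels still need correcting.

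**What to change.** Before the outcome is analysed, amend D.3 and E.2 as follows.

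1. Keep the ratio, but label it as share of Phase 2 use.
2. For H2c success, require also that Phase 2 mean UBMC/day is at most 50% of usual UBMC/day. Writing the share condition as S > U keeps it defined for a participant who smokes no UBMC.
3. Report study product/day as a fraction of usual use, and total products/day in both weeks, so that replacement, cutting down and added use can be told apart. The combined rule alone does not exclude cutting down.
4. Take usual use from the UBMC diary week. Handle lab-visit and abstinence days the same way in both weeks. Use screening cigarettes/day as the fallback or sensitivity reference when few clean diary days remain.
5. Reserve any substitution for study product use accompanied by a fall in UBMC use.
6. State whether H2c is scored on the Phase 2 diaries or on the Phase 3 task.

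The cost is wording only, since both weeks' counts are already collected. The H2c success rate may be somewhat lower, and the reference mean may be noisier where few clean days remain.

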## E. Statistical Methods

### 1. Power Analysis

Since our main goal is to evaluate the substitutability of menthol alternatives in the context of a menthol cigarette ban, statistical power is based on differences in abuse liability measures (Hypothesis 1a) and product substitution (Hypothesis 2c). Sample size estimates relied on means and standard deviations of data collected as part of a University of Vermont laboratory study examining the abuse liability of cigarettes containing different doses of nicotine. A sample size of 80 subjects has 81% power to detect decreases in product satisfaction of up to 50% compared to their usual brand (mean for UBMC 5.5, SD 1.3). In addition, a sample size of 80 participants has greater than 80% power to detect decreases of 68%–72% in the cigarette purchase task indices of maximum expenditure, maximum price and price sensitivity, similar to what we found in our laboratory study. This sample size also provides 81% power to estimate 80% use of the preferred alternate product more than half the time during Phase 2 with a 95% confidence interval of 66%–94%.

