**The goal of the proposed study is to examine the abuse liability and substitutability of plausible menthol cigarette alternatives.** Using an in-laboratory and *ad libitum* outpatient mixed design, current menthol cigarette smokers (N=135) will complete a three phase, 3-week study: in Phase 1, utilizing a randomized crossover design, participants will complete [4 smoking sessions], smoking a different product each session to examine each product's abuse liability, demand, and topography. Products will include participants' usual brand menthol cigarette (UBMC) as well as 3 commercially-available alternatives, including mFLC, mRYO product, [*and non-mentholated cigarette (nmC).*] Participants will complete one-week of daily diaries after smoking session 1 in phase 1 to assess their usage of usual brand menthol cigarette (UBMC). In Phase 2, to assess uptake, changes in subjective effects, and use over time, participants will [*select their preferred study product from Phase 1*] and be instructed to completely substitute the product for their UBMC for one week. Participants will complete daily diaries during this period to more accurately assess substitution and perceived effects in real-time. In Phase 3, participants will complete a final in-lab visit to assess the substitutability of [*their preferred product from Phases 1 and 2,*] under simulated ban conditions using a progressive ratio task. In all phases, multiple domains of abuse liability will be assessed, including product administration (in-lab topography and daily diary self-report measures), product liking/craving and withdrawal suppression (in-lab and daily diary self-report).

**Aim 1: To assess the abuse liability of menthol cigarette alternatives.** *H1a: Alternatives will [have similar use topography and significantly reduce nicotine craving/withdrawal similar to UBMC, but (H1b) UBMC will show significantly greater demand indices and liking/satisfaction compared to alternatives. H1c: Among alternatives, nmC will show the greatest demand and liking/satisfaction, followed by mFLC, and lastly mRYO.]*

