### 2. Data Analytic Plan

Statistical analyses will be performed using SAS 9.4 and an alpha of .05. Background measures will be summarized by product (UBMC, mFLC, mRYO, nmC), as appropriate. Continuous variables will be presented as mean  $\pm$  SD; categorical variables will be presented as counts and proportions. We will apply a transformation to normalize the distribution and stabilize the variance of the residuals where appropriate.

Hypotheses 1a and 1c: We will use Repeated Measures Analysis of Variance with Tukey-adjustment to examine differences between the alternatives and the UBMC in abuse liability assessed at each product lab session. Assuming statistically significant product differences, this post-hoc test will allow us to not only compare each product to the UBMC, but will also allow comparison of the alternative products with each other. Because product introduction in Phase 1 will be randomized using a Latin Square, a fixed effect for session and a random effect for sequence will be included in all analyses.

Hypothesis 2a: Product preference will be examined using a Chi-Square Test, comparing the proportions of participants choosing each alternate product for further use.

Hypothesis 2b: We will examine the trajectory of use behavior outcomes using Linear Mixed Model (LMM) regression analysis. We will employ a random intercept or slope parameter, as appropriate, and model the covariance structure for the repeated outcome measures, while accounting for potential confounders, including gender and baseline cigarettes/day.

Hypothesis 2c: This aim will be analyzed as a Chi-Square Test of Goodness of Fit to test the proportion of use compared to 80%.

Hypothesis 3: We will examine whether differences in product characteristics and changes in perceived effects collected via daily diary are associated with increased substitution of the alternate product over the seven-day period using generalized LMM regression analysis, similar to that outlined in H2b.

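### H2c is stated for the simulated ban (Phase 3), but its power and its only 50% rule belong to Phase 2 use, and its planned test names neither phase nor measure

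*Combined protocol and SAP*

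**What the plan says.** Section A, Aim 2 states the hypothesis: "H2c: Under simulated UBMC ban conditions, >80% of participants will substitute at least 50% of their UBMC use with study product".

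The ban simulation is placed in Phase 3. Section A describes the final visit as assessing the preferred product "under simulated ban conditions using a progressive ratio task". The Abstract and D.1 say the same, and D.2 titles that session "Simulated Menthol Cigarette Ban Using a Progressive Ratio Task (Phase 3)". In the task, UBMC puffs cost 10 clicks rising to 7,200, while study-product puffs always cost 10.

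E.1 says that "statistical power is based on differences in abuse liability measures (Hypothesis 1a) and product substitution (Hypothesis 2c)". Its H2c figure is then 81% power, with 80 participants, to "estimate 80% use of the preferred alternate product more than half the time during Phase 2", with a 95% interval of 66% to 94%.

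D.3 (Measures) gives one 50% rule: a ratio of study product to UBMC above 1, from Phase 2 diary use. For the progressive ratio task it gives only the proportion of reinforcers earned, with no cut-off per participant.

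On Phase 2, D.2 says: "Participants will be instructed to completely switch and exclusively use the study product during the 1-week time period". The product is supplied at no cost, at 1.2 to 1.

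E.2 says that H2c will be a chi-square goodness-of-fit test, to "test the proportion of use compared to 80"%. It gives no phase and no measure. The progressive ratio task is not named anywhere in E.2.

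**The concern.** E.1 calls substitutability in the context of a menthol ban the main goal. H2c is the only hypothesis in Aims 1 to 3 worded for that condition. The stated power belongs to a different outcome, measured in a different phase under different incentives.

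The analyst has two routes, and both fail as the plan stands:

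- **Follow E.1 and the D.3 rule (Phase 2).** A week with free product, an instruction to switch and no restriction on UBMC would be reported as behavior under a ban. The progressive ratio task would then have no stated analysis.
- **Follow the wording of H2c (Phase 3).** There is no rule for when a participant counts as having substituted at least half, and no power statement for that outcome.

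Because E.2 does not choose, the choice could be made after both results are known. The work is meant to inform FDA on a ban, so the distinction affects what can be claimed.

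**Working it through.** **1. The places side by side**

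| Element of H2c | Phase it belongs to | Where |
|---|---|---|
| Condition (simulated ban) | Phase 3 | Abstract, A, D.1, D.2 |
| Power | Phase 2 | E.1 |
| 50% rule (ratio > 1) | Phase 2 | D.3 |
| Test against 80% | not stated | E.2 |

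The exploratory paragraph of E.2 links product substitution to Phase 2, and E.1 uses the same term for H2c. This leans toward a Phase 2 analysis without settling it.

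**2. Reproducing the plan's 81%**

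Inputs: n = 80 and 80% (E.1), alpha 0.05 (E.2; two-sided assumed). With X participants meeting the rule, 64 are expected to meet it and 16 not to. The test statistic is

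(X − 64)²/64 + (X − 64)²/16 = (X − 64)²/12.8, compared with 3.84 (1 df).

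- X = 57 or 71: 49/12.8 = 3.83, not rejected.
- X = 56 or 72: 64/12.8 = 5.00, rejected.

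So the test rejects at 56 or fewer, or at 72 or more. The exact binomial tails at a true 80% are 0.0217 (lower) and 0.0131 (upper).

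- Power at a true 66%: P(X ≤ 56) = 80.8%. This matches the stated 81%.
- 95% Wald interval around 80%: 0.80 ± 1.96 × √(0.80 × 0.20/80) = 0.80 ± 0.088, or 71.2% to 88.8%. The Wilson interval is 70.0% to 87.3% and the Clopper-Pearson interval 69.6% to 88.1%. None gives 66% to 94%.

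The 81% therefore reproduces if 66% is taken as the alternative to a null of 80%. That is power to find a share below 80%, whereas H2c claims a share above it.

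**3. Power in the direction of H2c**

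The documents give no expected Phase 3 proportion, so the true share is an assumption and is shown as a range. With n = 80, rejection in the upper tail needs at least 72 of 80 (90% observed).

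| True share | Power, P(X ≥ 72) |
|---|---|
| 85% | 13% |
| 88% | 37% |
| 90% | 59% |
| 91% | 71% |
| 92% | 81% |
| 94% | 95% |

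**4. Whether the two phases could stand in for each other**

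Cumulative UBMC clicks from the D.3 schedule: 10, 170, 490, 1,130, 2,410, 4,810, and on to 26,410 for ten.

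Assume that the cap of 10 reinforcers covers both products and that all 10 are earned. Falling below 50% study product then takes six UBMC reinforcers: 10 + 160 + 320 + 640 + 1,280 + 2,400 = 4,810 clicks. The other four, from the study product, cost 4 × 10 = 40.

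A 50% share in Phase 3 is thus shaped by the cost schedule. A 50% share in Phase 2 is shaped by the instruction and free supply. They are different quantities.

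**The case against.** The strongest reply is that E.2 labels its test as Hypothesis 2c, and Aim 2 defines that hypothesis under ban conditions. Read together, the chi-square test is the planned Phase 3 analysis, with the proportion of reinforcers earned as its outcome. This reading is open. A reader might infer that the ban claim must come from Phase 2 and that Phase 3 yields no planned result. The documents do not support that as fact, because E.2 is silent on phase. The reply does not remove the problem: on this reading H2c still lacks a rule per participant and a power basis.

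Other points that stand, at least in part:

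- H2c speaks of replacing UBMC use, which fits diary counts more naturally than two-puff reinforcers. The section on study weaknesses lists both the diary and the progressive ratio task as substitution measures. Phase 2 is a legitimate measure; it is not a measure under a ban.
- That UBMC remains available in Phase 2 is implied by the diary counts and the ratio, not stated.
- A reader might infer that Phase 2 use shows only compliance and price, or try to size the inflation. Participants can record UBMC use, so it is not only that, and the documents give no figure for the effect of the instruction. No size is claimed here.
- The Phase 3 cross-price task also bears on substitution as UBMC prices rise, but its choices are hypothetical and E.2 does not link it to H2c.

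**Conclusion.** The inconsistency holds and is more than a missing detail: the power offered for H2c belongs to an outcome other than the one H2c states. This conclusion is textual and does not depend on the arithmetic.

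The arithmetic adds that the 81% cannot be carried over by changing the phase label. It matches power to detect 66% against 80%. For H2c's direction, 80 participants give 13% power at a true 85%, 59% at 90% and 81% at 92%. These figures assume 80 analyzable participants, a two-sided 0.05 test and one yes/no outcome per participant. The true Phase 3 share is unknown.

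**What to change.** In E.1 and E.2, tie H2c to Phase 3:

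- Define the outcome as the proportion of participants earning at least 50% of their earned progressive ratio reinforcers from the study product. State the denominator when fewer than 10 are earned, the handling of a participant who earns none, and whether the cap covers both products.
- Report the UBMC breakpoint (highest requirement completed) alongside, because the schedule itself favors the study product.
- Do not present the first choice, where both products cost 10 clicks, as an unrestricted reference. Participants are told the escalation in advance.
- Replace the 81% statement with power for a share above 80%, shown over a range such as the one above.
- Keep Phase 2 use as a separately named outcome, substitution under instruction and free supply, and do not describe it as behavior under a ban.

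If the investigators prefer Phase 2 as the H2c measure, remove the ban condition from H2c, restate its power in the same way, and add a stated analysis of the progressive ratio task.

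Cost: edits to the hypothesis, power and analysis text. The progressive ratio data are already scheduled at Visit 5. The price is a narrower Phase 2 claim and a less favorable stated power.
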